8.2.1. Ordinal Scale Outcomes (Key Secondary Outcome Measure)

For the analysis of the key secondary outcome measure, the distribution of the 8-point ordinal clinical status scale with 8 categories at Study Visit Day 15 (not necessarily actual study day 15), the outcome will be analyzed using a proportional odds model with treatment arm and disease severity as covariates. The treatment odds ratio estimated from the model will be presented along with the p-value (Table 25). The Study Visit Day 15 clinical status score will be depicted graphically using shifted bar plots; the outcomes will be presented by baseline ordinal score and treatment group (Figure 13). In addition to the subgroup analyses, the main analysis will be

repeated including a treatment * disease severity interaction term, where the interaction term p-value will be reported for the interaction model.

Multiple supplemental analysis of this key secondary outcome will be performed. Time to improvement by at least one category in the clinical status 8-point scale (see Section 3.3). The log rank test will be performed using a Cox proportional hazards model to test whether the curves differ between treatment arms. The median time to event and CI in each treatment group will be summarized along with the treatment hazard ratio estimate and log rank p-value (Table 27). Differences in time-to-event endpoints by treatment arm will be summarized with Kaplan-Meier curves (Figure 16). Number at risk, hazard ratio and log rank p-values will be presented on the figures. The analyses (and tabular and graphical summaries) will be repeated using the outcome of time to improvement in two categories of the ordinal scale defined in Section 3.3. In addition, a subgroup analysis time to improvement among subjects enrolled with a clinical score of 7 will be performed using the retreatment censoring plan.

The above analyses will be repeated with the modification to the ordinal scale described in Section 4.3 (Table 28).

The number and proportion of subjects along with 95% confidence intervals by category of clinical status will be presented by treatment arm at Study Visit (not necessarily actual) Days 1, 3, 5, 8, 11, 15 and 29 (Table 33). Change from baseline will also be summarized at Days 3, 5, 7, 11, 15, 22, and 29 (Table 35). A figure will present stacked bar charts by day with side by side bars for each treatment arm (Figure 25). Histograms will be generated to display the ordinal scale value distributions over time in each treatment group (Figure 26).

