 - Evaluate if subject is neutropenic (absolute neutrophil count <1000 cells/ μL) ($<1.0 \times 10^3/\mu\text{L}$ or <1.0 GI/L) and/or lymphopenic (absolute lymphocyte count <200 cells/ μL) ($<0.20 \times 10^3/\mu\text{L}$ or <0.20 GI/L)
 - ALT and AST
 - Assess if ALT or AST > 5 times the upper limit of normal.
 - Creatinine (and calculate eGFR).
 - Determine if eGFR < 30 ml/min as these subjects are not eligible. Also, subject receiving hemodialysis or hemofiltration are not eligible.
 - Any automated calculation by the clinical laboratory or published formula for this calculation is acceptable. The site should select a formula to be used for all subjects enrolled at the site for the duration of the study.
- Urine or serum pregnancy test (in women of childbearing potential).

Clinical screening laboratory evaluations will be performed locally by the site laboratory. The volume of venous blood to be collected is presented in Table 3.

The overall eligibility of the subject to participate in the study will be assessed once all screening values are available. The screening process can be suspended prior to complete assessment at any time if exclusions are identified by the study team.

Study subjects who qualify will be randomized in the Advantage eClinical system, and all others will be registered as screen failures. The ordinal scale and the NEWS should be done at the time of randomization; the site will need this data to randomize the subject in eClinical. The study team has 24 hours to complete other Day 1 baseline assessments prior to the first study product administration including the collection of OP swab and blood and completing or recording a baseline physical examination that was done.

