Table 6 displays five scenarios considered for outcome probabilities in the control arm for sample size determination. There is significant uncertainty with these assumptions given the limited data available. Table 6 shows a range of sample sizes for odds ratios ranging from 1.25 to 2.5 for 85% power. For 90% power, increase the sample size by 17%. Table 8 displays the probabilities of being in different categories of the ordinal scale under an odds ratio of 1.75. A total sample size of 396 gives approximately 85% power to detect an odds ratio of 1.75 using a 2-tailed test at level $\alpha = 0.05$. The categories of the 8-point ordinal scale are:

- Death;

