9.4.3 Analysis of the Secondary Endpoint(s)

- 7) The ordinal scale will be used to estimate a proportional odds model by disease strata. The hypothesis test will perform a stratified test to evaluate whether the common odds ratio for treatment is equal to one. The distribution of severity results will be summarized by treatment arm as percentages. Efforts to minimize loss-to-follow-up will be considerable. However, small amounts of missing data may occur. In such cases, subjects without final outcome data will be excluded from the analysis. Sensitivity analyses will evaluate the impact of making different assumptions about missing observations. These analyses will be defined in the SAP.
- 8) Differences in time-to-event endpoints (e.g., time to at least a one category improvement in ordinal scale) by treatment will be summarized with Kaplan-Meier curves and 95%

confidence bounds. The same procedure will be used to compare time to at least a two-category improvement.

- 9) Change in ordinal scale at specific time points will be summarized by proportions (e.g., proportion who have a 1-, 2-, 3-, or 4-point improvement or 1-, 2-, 3-, 4-point worsening).
- 10) Duration of event (e.g., duration of mechanical ventilation) will be summarized according to median days with quartiles.
- 11) Binary data (e.g., incidence of new oxygen use) will be summarized as a percent with 95% confidence intervals. Comparisons between arms will be presented as differences in proportions with 95% confidence intervals.
- 12) Categorical data (e.g., 28-day mortality or ordinal scale by day) may be summarized according to proportions by category and/or odds ratios with confidence intervals.

Procedures for handling missing data, including informative censoring (e.g., a missing duration of oxygen use endpoint due to a death), will be described in the SAP.

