4.2.3. Method of Assigning Subjects to Treatment Groups (Randomization)

Enrollment and randomization of subjects is done online using the enrollment module of Advantage eClinical[®].

Eligible subjects will be randomized and assigned in a 1:1 ratio to either baricitinib + remdesivir or remdesivir, with stratification by site and disease severity by ordinal scale (Moderate disease [4 or 5 on the ordinal scale] or Severe disease [6 or 7 on the ordinal scale]). The randomization is based on a variable blocked scheme to provide an approximately balanced allocation to the treatment groups during the study. If arms are added or removed later in the study, randomization will continue in an equal allocation manner.

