5. SAMPLE SIZE CONSIDERATIONS

Sample Size for Primary Analysis

The log-rank test will be used to compare treatment arms with respect to time to recovery. For the log-rank test, the two key determinants of power are the total number of events (i.e., recoveries) E and the treatment-to-control ratio of the rate of recovery. The number of events required for power $1 - \beta$ to detect a recovery rate ratio of θ using a two-tailed test at $\alpha=0.05$ is approximately

$$E = \frac{4(1.96 + z_{\beta})^2}{\{\ln(\theta)\}^2},$$

where z_{β} is the $100(1 - \beta)$ th percentile of the standard normal distribution.

The force of recovery (sometimes loosely referred to as the “recovery ratio”) is the analogue of the hazard ratio and the term “recovery rate ratio” is the analogue of the hazard ratio in this setting. A recovery rate ratio of 1.31 was reported in Cao, Wang, Wen et al. (2020) for a lopinavir/ritonavir trial that used time to improvement by 2 categories as primary endpoint. A preliminary review of data from ACTT-1 demonstrated a recovery rate ratio 1.312. It is unlikely the second component of treatment will have a similar effect size. Therefore, a recovery ratio of 1.25 is assumed for this trial. A total of 723 recoveries are needed for a recovery ratio of 1.25 with 85% power. The study will accrue until approximately 723 recoveries have been achieved. The date of study closure will be estimated based on enrollment rate and recovery/enrollment percentages. If approximately 70% of participants recover, the total sample size will be 1032.

See Section 9.2 of Appendix B of the study protocol for discussions on the sample size calculations for the key secondary outcome.

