To perform a stratified Cox proportional hazards model for the final analysis and generate the treatment arm hazard ratio along with its confidence interval, the following pseudocode will be used. For any unstratified analyses, code can be used after the removal of the `strata ... ;` line and strata variable in the `class` statement.

```
proc phreg data=dataset;
  class StrataVariable(ref=StrataLabel)
  TreatmentVariable(ref=RemdesivirLabel);
  model TimeVariable * CensorVariable(1) = TreatmentVariable;
  strata StrataVariable;
  hazardratio TreatmentVariable / diff=ref cl=Wald;
  ods output HazardRatios = HRest;
run;
```

The following SAS pseudocode will be used to perform the final proportional odds model with treatment arm and disease severity as covariates and to generate the treatment odds ratio, p-value, and predicted probabilities of the ordinal scale levels by treatment arm and disease severity:

```
proc logistic data=dataset
  plots (only)=effect (x=ResponseVariable
    sliceby=DiseaseSeverityVariable*TreatmentVariable individual connect);
  class DiseaseSeverityVariable (param=ref ref=ModerateLabel)
    TreatmentVariable (param=ref ref=RemdesivirLabel);
  model ResponseVariable = TreatmentVariable StrataVariable;
  oddsratio TreatmentVariable;
  ods output OddsRatiosWald = ORest;
run;
```

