6.4. Covariates and Subgroups

Subgroup analyses for the main efficacy outcomes (i.e. the primary and key secondary analyses) will evaluate the treatment effect across the following subgroups:

- Geographic region:
 - US sites; Non-US sites
 - North American sites; Asian sites; European sites
- Duration of symptoms prior to enrollment
 - Quartiles
 - ≤ 10 days; > 10 days
 - \leq Median; $>$ Median
- Race (White; Black/African American; Asian; Other)
- Comorbidities
 - None; Any
 - None, One, Two or more
 - Obese; Non-Obese
- Age (<40 ; 40-64; 65 and older),
- Sex (Female; Male),
- Severity of disease
 - Randomization stratification: Moderate (ordinal 4/5); Severe (ordinal 6/7).
 - Actual disease severity at baseline: Moderate (ordinal 4/5); Severe (ordinal 6/7)
Note these analyses will only be performed if at least one subject is erroneously randomized into the incorrect disease severity stratum.
 - Baseline ordinal scale category: 4; 5; 6; 7

Additionally, main analyses of all secondary efficacy outcomes will evaluate the treatment effect across the following subgroups:

- Duration of symptoms prior to enrollment (\leq Median; $>$ Median)
- Severity of disease

- Randomization stratification: Moderate (ordinal 4/5); Severe (ordinal 6/7).
- Actual disease severity at baseline: Moderate (ordinal 4/5); Severe (ordinal 6/7)

Note these analyses will only be performed if at least one subject is erroneously randomized into the incorrect disease severity stratum.

- Baseline ordinal scale category: 4; 5; 6; 7

There will also be a sensitivity analysis of the primary, key secondary, and mortality outcomes to evaluate the effect of concomitant therapy including experimental treatment and off-label use of marketed medications that are intended as treatment for COVID-19 and are given to patient prior to and during the study. A blinded review of the concomitant medication data will be performed by the medical monitor to identify medications that fall into any of the following categories of “Medications of Interest”:

- Antivirals
 - Protease inhibitors
 - Polymerase inhibitors
- Potential Treatments for COVID-19
 - Hydroxychloroquine/Chloroquine
 - Other
- Corticosteroids
- Other anti-inflammatory drugs
 - Monoclonal Antibodies Targeting Cytokines
 - Other Biologic Therapies

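### The key secondary Day 15 model adjusts for baseline status only as moderate (4/5) versus severe (6/7), although the four-level baseline score is already recorded; adjusting for it is a cheap efficiency gain

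*SAP*

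**What the plan says.** SAP 8.2.1 analyses Day 15 status as follows: "the outcome will be analyzed using a proportional odds model with treatment arm and disease severity as covariates". The code in SAP 6.1 agrees: "model ResponseVariable = TreatmentVariable StrataVariable". SAP 4.2.3 defines severity in two levels, "Moderate disease [4 or 5 on the ordinal scale] or Severe disease [6 or 7 on the ordinal scale". Protocol Appendix B 9.4.3 sets the same structure: "The ordinal scale will be used to estimate a proportional odds model by disease strata".

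The four-level score exists for every randomised subject. Protocol Appendix B 8.1.1 states "The ordinal scale and the NEWS should be done at the time of randomization", and the site needs it in order to randomise.

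For this outcome the SAP uses the four-level score in three places:
- a subgroup factor in SAP 6.4, "Baseline ordinal scale category: 4; 5; 6; 7";
- the Day 15 plot by baseline score (SAP 8.2.1);
- a treatment-by-score interaction row in Table 25.

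The covariate-adjusted row of Table 25 lists age, symptom duration, d-dimer and CRP, but not the baseline score. Nowhere is one pooled odds ratio planned with the score as a main effect.

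**The concern.** The outcome is the later value of a scale whose starting value is known, and that starting value would ordinarily be the first covariate to consider. The two-level term treats 4 and 5 as alike, although only 5 is on oxygen. It also treats 6 and 7 as alike, although only 7 is on invasive ventilation or ECMO.

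If prognosis differs within either pair, the two-level model averages over that difference. The odds ratio is non-collapsible, so the averaged value lies closer to 1 than the odds ratio conditional on score, and the test has less power. This is a change of target, not bias, and type I error is unaffected. The subgroup and interaction outputs do not fill the gap, because each gives score-specific effects and not one overall comparison.

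**Working it through.** **1. The plan's own figure.** Protocol Appendix B 9.2 states "A total sample size of 396 gives approximately 85% power to detect an odds ratio of 1.75". Its formula is N = 12(z_{α/2} + z_β)² / [λ²(1 − Σp_i³)], with p_i averaged over the arms. For Scenario 1 and odds ratio 1.75:
- (1.960 + 1.036)² = 8.98;
- λ² = (ln 1.75)² = 0.3132;
- 1 − Σp_i³ = 0.873;
- N = 12 × 8.98 / (0.3132 × 0.873) = 394.

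This agrees with 396 to within rounding. The formula uses no covariates.

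**2. Power at the planned size.** SAP 5 states "If approximately 70% of participants recover, the total sample size will be 1032". From the same formula, power = Φ(λ√[N(1 − Σp_i³)/12] − 1.96). At N = 1032:

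| Odds ratio | Scenario 1 | Scenario 5 |
|---|---|---|
| 1.25 | 49.9% | 52.8% |
| 1.40 | 83.7% | 86.4% |
| 1.50 | 94.2% | 95.8% |
| 1.75 | 99.8% | 99.9% |

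Efficiency therefore matters only for effects below 1.75. The value 1.40 is not in the documents. It is used because power there is close to 85% at this N.

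**3. Two-level versus four-level adjustment.** Both proportional odds models were fitted to expected cell counts, so there is no simulation error.
- From the documents: 1:1 allocation, N = 1032, two-sided 5%, and control margins fixed to Scenario 1 or 5 of Protocol Appendix B Table 6.
- Assumed, because the documents do not give them: mix of scores 4/5/6/7 of 25/25/25/25, 15/50/20/15 or 10/55/30/5%; severe-versus-moderate odds ratio 3 or 8; within-stratum odds ratio for a worse outcome from 1 to 8.

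Gain in power, in percentage points, by within-stratum odds ratio:

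| Treatment OR | 1 | 1.5 | 2.5–4 | 5–8 | Two-level power |
|---|---|---|---|---|---|
| 1.25 | 0 | 0.2–0.6 | 1.1–6.3 | 3.1–12.4 | 35–52% |
| 1.40 | 0 | 0.2–0.5 | 1.1–6.1 | 3.2–13.5 | 66–86% |
| 1.50 | 0 | 0.1–0.3 | 0.7–4.0 | 2.0–10.0 | 81–96% |
| 1.75 | 0 | <0.1 | 0.04–0.6 | 0.1–2.1 | 97.4–99.9% |

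The top figures need the equal mix and a within-stratum odds ratio of 8. With mix 10/55/30/5 and the same 8, the gain at 1.40 is 5.0–6.4. At a within-stratum odds ratio of 2.5 it is 1.1–2.6 across all mixes.

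**4. One case in full.** Scenario 1, mix 15/50/20/15, severity odds ratio 3, within-stratum 2.5, treatment 1.40:
- Two-level: odds ratio 1.385, SE 0.1154; ln 1.385 / 0.1154 = 2.82; power Φ(2.82 − 1.96) = 80.5%.
- Four-level: odds ratio 1.400, SE 0.1163; ln 1.400 / 0.1163 = 2.89; power Φ(2.89 − 1.96) = 82.5%.
- Equivalent saving: 1 − (2.82/2.89)² ≈ 5% of N, or about 50 subjects.

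The standard error rises slightly. The gain comes from the larger target odds ratio.

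**5. Simulation.** 4000 trials per setting, with the same scenario, mix and severity gap, and within-stratum odds ratios 1, 2.5 and 5. Type I error was 5.2–5.3% (two-level) and 4.8–5.2% (four-level), with Monte Carlo SE 0.35 points. Power at 1.40 was 83.0 vs 83.0%, 79.9 vs 82.0% and 76.3 vs 81.6%. With 3% of subjects randomised in the wrong stratum and both terms in the model, four-level type I error was 5.3–5.4% and power was 82.3, 83.3 and 81.9%, against 81.8, 81.3 and 75.8% for two-level.

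**The case against.** The filed model is valid. It matches the randomisation factor, the protocol and the ACTT-1 model, and SAP version 3.0 sought consistency across stages. At the worked odds ratio of 1.75 the gain is negligible. Its size elsewhere depends on inputs the documents do not contain, and the range starts at zero. The confidence interval on the log scale gets no narrower. SAP 6.8 gives the key secondary no multiplicity control, so within this SAP the benefit is to a nominal p-value; adjusted testing is left to an Addendum (SAP 2.1) that was not available. All of this stands, and it limits the point to efficiency.

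Two technical objections stand in part:
- The calculations generate data from proportional odds in the four scores, which is the model being recommended. A check with treatment effects that differed across scores did not reverse the gain, but non-proportional odds across baseline scores were not examined.
- If stratum and score are both fitted, only mis-stratified subjects identify the stratum coefficient. With a single such subject in an end category it can diverge. The treatment estimate was unaffected when this was tried, but the SAP would need a handling rule.

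Neither objection removes the case for adjusting for a baseline value that is already in hand.

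**Conclusion.** The point holds as an improvement worth making, not as an error or a conflict. No setting examined lost power. Where the scores within a stratum share prognosis, nothing is gained. With a within-stratum odds ratio of 2.5 to 4 and a treatment odds ratio of 1.25 to 1.50, the gain is roughly 1 to 6 points. At 1.75 it is at most about 2. These sizes rest on the assumed baseline mixes and prognostic gaps and on proportional odds. Confidence in the size is medium. The direction follows from non-collapsibility.

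**What to change.** Decide before unblinding, because finer adjustment shifts the target odds ratio slightly and a later choice could look selective.

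- **Option (a):** add baseline score (4, 5, 6, 7) as a factor in the key secondary model and keep the randomised stratum, so that mis-stratified subjects are handled. State that the stratum term is dropped if nobody is mis-stratified or if its coefficient cannot be estimated. Each score lies inside one stratum, so the protocol strata are refined, not discarded. The cost is a documented change to SAP 8.2.1 and 6.1 and to Protocol Appendix B 9.4.3, and a model that differs from ACTT-1.
- **Option (b), the minimum:** keep the filed main model and pre-specify the option (a) model as one named supportive row in Table 25. The cost is one SAP sentence, one line of code and one table row.

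Neither option needs new data. Leave the primary log-rank test and its tables as filed.

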8.2.2. NEWS

The median time to discharge or to a NEWS of ≤ 2 and CI will be summarized by treatment group (Table 37). The hazard ratio and log rank p-values will be provided with the summaries. Differences in time-to-event endpoints by treatment arm will be summarized with Kaplan-Meier curves. Number at risk, hazard ratio and log rank p-values will be included on the figures (Figure 27).

The mean, standard deviation (SD), median, minimum, and maximum NEWS at Baseline and Study Visit (not necessarily actual) Days 3, 5, 8, 11, 15 and 29 will be presented by treatment arm as well as change from baseline at each post-Day 1 visit (Table 40). A figure with mean and SD over time will also be presented by treatment arm (Figure 32).

Subject listings of NEWS responses (overall and individual components) by day will be generated (Listing 6).

8.2.3. Days of Oxygenation

Duration of oxygenation days will be summarized in a table using medians and quartiles by treatment arm (Table 42). This will only include subjects in category 5, 6, or 7 at randomization. Analyses will be performed in the ITT and As Treated populations. Bee swarm plots of oxygen days by treatment arm will be generated, where subjects whose days are imputed to the maximum of 28 days due to death are grouped separately from subjects who do not die (Figure 33).

8.2.4. Incidence of New Oxygen use

The incidence and duration of new oxygen use will be analyzed by treatment arm. This will only include subjects in category 4 at randomization. New use will be identified by a post-enrollment score of at least 5; the number of subjects reporting new use and the incidence rate (and CI) will be reported.

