Appendix B - ACTT-2: Baricitinib/Remdesivir vs Remdesivir

clinical outcome measure of Day 2 is captured with the worst being death followed by ECMO, mechanical ventilation, etc. The Day 2 measurement is assessed as occurring anytime in that 24-hour period (00:00 to 23:59).

It is important to capture all deaths that occur during the study as this is one of the outcomes of the study. Death is a category on the ordinal scale. If a subject dies during the study, the site will need to complete an ordinal scale assessment for the day after death. If a subject dies within the window of the final study visit (i.e., Day 29 \pm 3 days), complete an ordinal scale assessment on the day after death.

For more information about the data collected for the ordinal scale, see the MOP.

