3.3.8. Days of Oxygen

Oxygen days will be defined as the number of days where the clinical status score is equal to 5, 6, or 7. After discharge, the Post-Discharge Supplemental Oxygen CRF question regarding days of oxygenation (including ECMO, invasive ventilation, non-invasive ventilation, high-flow oxygen devices, and all other oxygen delivery devices) will be used. The total number of days will be the sum of all reported days, regardless of whether the days occur consecutively or in disjoint intervals. See Section 6.5 for the plan for handling subjects who do not have data through Day 29 or die prior to Day 29.

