4.3. Efficacy and Safety Variables

For each study day while the patient is hospitalized, the clinical status will be recorded on an 8-point ordinal scale as follows:

- Day 1 – The clinical assessment at the time of randomization.
- Day 2 + - The most severe assessment occurring from midnight to midnight (00:00 to 23:59) of the prior day (e.g., the value recorded on Day 3 will be the most severe outcome that occurred on Day 2).

where the clinical status scale is defined as follows:

- 8. Death;

7. Hospitalized, on invasive mechanical ventilation or ECMO;
6. Hospitalized, on non-invasive ventilation or high flow oxygen devices;
5. Hospitalized, requiring supplemental oxygen;
4. Hospitalized, not requiring supplemental oxygen- requiring ongoing medical care (COVID-19 related or otherwise);
3. Hospitalized, not requiring supplemental oxygen - no longer requires ongoing medical care;
2. Not hospitalized, limitation on activities;
1. Not hospitalized, no limitations on activities

A modified version of the ordinal scale will be used in sensitivity analyses of the primary and secondary outcomes. The modified scale will be as follows:

8. Death;
7. Hospitalized, on invasive mechanical ventilation or ECMO;
6. Hospitalized, on non-invasive ventilation or high flow oxygen devices;
5. Hospitalized, requiring supplemental oxygen;
4. Hospitalized, not requiring supplemental oxygen- requiring ongoing medical care (COVID-19 related or otherwise);
3. Not hospitalized, limitation on activities;
2. Hospitalized, not requiring supplemental oxygen - no longer requires ongoing medical care; or Not hospitalized, no limitations on activities.

That is, category 1 and 3 of the original scale will be combined into the lowest category.

NEWS has demonstrated an ability to discriminate subjects at risk of poor outcomes. This score is based on 7 clinical parameters (see Section 8.1.2.3 in Appendix B of the study protocol). This should be evaluated at the first assessment of a given study day and prior to administration of study product. The 7 parameters can be obtained from the hospital chart using the last measurement prior to the time of assessment and a numeric score given for each parameter (e.g., a RR of 9 is one point, oxygen saturation of 92 is two points). This is recorded for the day obtained. i.e., on Day N, the Day N score is obtained and recorded as the Day N score.

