 - If the subject's clinical status scale is 6 at the last observed assessment, then the subject will be considered to be on non-invasive ventilation/high-flow oxygen through Day 29. The endpoint will be total days when assessments are available plus all imputed days following the last observed assessment.
 - If the subject is not on non-invasive ventilation/high-flow oxygen at the last observed assessment, then the subject will be considered to not be on non-invasive ventilation/high-flow oxygen for the remainder of follow-up. Thus, no additional imputed days will be added to the number of days recorded on available assessments.

- Days of ventilation/ECMO:
 - If the subject's clinical status scale is 7 at the last observed assessment, then the subject will be considered to be on ventilation/ECMO through Day 29. The endpoint will be total days when assessments are available plus all imputed days following the last observed assessment.
 - If the subject is not on ventilation/ECMO at the last observed assessment, then the subject will be considered to not be on ventilation/ECMO through Day 29. Thus, no additional imputed days will be added to the number of days recorded on available assessments.
- Days of Oxygen:
 - If the subject's clinical status score is 5, 6, or 7 at the last observed assessment, then the subject will be considered to be on oxygen through Day 29. The endpoint will be total days when assessments are available plus all imputed days following the last observed assessment.
 - If the subject is not on oxygen at the last observed assessment, then the subject will be considered to not be on oxygen through Day 29. Thus, no additional imputed days will be added to the number of days recorded on available assessments.
- Days of Hospitalization
 - If the subject is discharged and no further hospitalization data are available, then the subject will be assumed to not have been readmitted. Thus, no additional imputed days will be added to the number of days recorded on available assessments. If a subject dies while hospitalized, the number of days of hospitalization will be imputed as 28 days.

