8.2.6. Incidence of New Non-Invasive Ventilation/High-Flow Oxygen

The incidence and duration of new Non-Invasive Ventilation/High-Flow Oxygen use will be analyzed by treatment arm. This will only include subjects in category 4 or 5 at randomization. New use will be identified by a post-enrollment score of 6. The number of subjects reporting new use and the incidence rate (and CI) will be reported.

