8.2.8. Incidence of New Invasive Mechanical Ventilation/ECMO

The incidence and duration of new Invasive Mechanical Ventilation/ECMO use will be analyzed by treatment arm. This will only include subjects in category 4, 5, or 6 at randomization. New use will be identified by a post-enrollment score of 7. The number of subjects reporting new use and the incidence rate (and CI) will be reported.

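### The SAP's rule for new oxygen use (any later score of at least 5) also takes in score 8, so a category-4 patient who dies with no recorded 5, 6 or 7 is counted as a new oxygen user

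*SAP*

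**What the plan says.** SAP 8.2.4 sets the population, "This will only include subjects in category 4 at randomization", and the event rule, "New use will be identified by a post-enrollment score of at least 5". In SAP 3.2 and 4.3 the top of the scale, 8, is death.

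Three other parts of the SAP describe being on oxygen without score 8:

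- 3.3.8: "Oxygen days will be defined as the number of days where the clinical status score is equal to 5, 6, or 7".
- 6.5, which carries oxygen use forward to Day 29 when follow-up is incomplete: "If the subject's clinical status score is 5, 6, or 7 at the last observed assessment, then the subject will be considered to be on" (the rule then names oxygen).
- 8.2.3: the oxygen-days summary takes patients in category 5, 6 or 7 at randomization.

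The two parallel incidence outcomes use single scores. In 8.2.6 it is "New use will be identified by a post-enrollment score of 6", and in 8.2.8 it is "New use will be identified by a post-enrollment score of 7".

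Death is a recorded score. Protocol Appendix B, 8.1.2.2 states: "If a subject dies during the study, the site will need to complete an ordinal scale assessment for the day after death".

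The Table 42 shell has a block for patients not on oxygen at baseline. Its programming note restricts the oxygen-days statistics in that block to patients with new use. One row in the block includes imputed days for patients who died.

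**The concern.** A program that applies the 8.2.4 rule literally will flag every category-4 patient with a recorded 8. For most deaths this changes nothing, because a 5, 6 or 7 will have been recorded first. It matters when none was. The patient is then reported as having started oxygen on the strength of the death alone.

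Two outputs are exposed. One is the incidence of new oxygen use, a listed secondary outcome. The other is the duration summary, because the same flag decides who enters it. SAP 8.2.3 speaks of oxygen days set to a maximum of 28 because of death. If that is carried into the new-use block, a patient with no recorded oxygen use would contribute the longest possible duration.

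**Working it through.** The plan gives no figure for this outcome, so there is nothing to reproduce. The check is a comparison of definitions, followed by an illustration on assumed counts.

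**1. Scores covered by each rule**

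| Rule | Scores | Counts death? |
|---|---|---|
| New oxygen use (8.2.4) | 5, 6, 7, 8 | Yes |
| On oxygen (3.3.8, 6.5) | 5, 6, 7 | No |
| New non-invasive ventilation/high-flow (8.2.6) | 6 | No |
| New invasive ventilation/ECMO (8.2.8) | 7 | No |

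{5, 6, 7, 8} minus {5, 6, 7} leaves {8}. Death is the whole difference between the new-use rule and the SAP's own oxygen definition.

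**2. Can an 8 occur with no 5, 6 or 7 on record?** Yes, by two routes.

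- *After discharge.* Protocol Appendix B, 8.1.2.2 schedules scores for discharged patients only on Days 15, 22 and 29. A category-4 patient can go home and die between these visits, and the next score is the 8.
- *Within one hospital day.* SAP 4.3 records "The most severe assessment occurring from midnight to midnight (00:00 to 23:59) of the prior day". A patient who goes from no oxygen to death inside one calendar day shows only the 8.

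**3. Effect on incidence.** Let n be the category-4 patients in an arm and d those who die with no recorded 5, 6 or 7. Removing score 8 lowers that arm's incidence by 100 × d/n percentage points. The documents give neither n nor d. Assuming n of 50 to 100 and d of 0 to 3:

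| d | n = 50 | n = 75 | n = 100 |
|---|---|---|---|
| 0 | 0 | 0 | 0 |
| 1 | 2.0 | 1.3 | 1.0 |
| 2 | 4.0 | 2.7 | 2.0 |
| 3 | 6.0 | 4.0 | 3.0 |

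The difference between arms changes only if d/n differs between them.

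**4. Effect on duration.** The d patients join the row that includes imputations for deaths. They do not enter the companion row, which is limited to survivors. Whether they carry 28 days is unclear. SAP 8.2.3 refers to that imputation, but the oxygen-days rule in 6.5 does not state it.

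**5. What does not move.** The primary outcome depends on first reaching a score of 1, 2 or 3. The key secondary outcome uses the Day 15 score itself. Neither uses the new-oxygen flag.

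**The case against.** The best defence is that the threshold may be deliberate. The SAP's oxygen-duration summaries already treat death as the worst result, through the 28-day imputation and the Table 42 row for it, and a rule that takes in score 8 fits that convention. This is possible, but nothing in 8.2.4 or the Table 42 shell says that a composite is meant, and the section is titled as oxygen use.

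A second argument stands in full. A category-4 inpatient who starts oxygen and dies on the same calendar day is recorded only as 8. For that patient the current rule gives the right answer, and a bare change to 5, 6 or 7 would lose a true new user. The documents do not show whether this case or the post-discharge case is more common, so the fix has to handle both.

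A reader might also infer that this wording is what makes the three incidence outcomes non-comparable. The documents do not support that. The outcomes already differ in population (category 4; 4 or 5; 4, 5 or 6) and in form (a threshold against single scores). A patient who goes from 4 straight to 7 counts for oxygen and for invasive ventilation but not for non-invasive ventilation. Removing score 8 makes the handling of death consistent, and no more than that.

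Finally, little rests on the result. SAP 6.8 plans no multiplicity adjustment for secondary outcomes, and 8.2.4 asks for an incidence and interval with no test between arms. Deaths also appear in Tables 24, 33 and 64, and individual scores in Listing 5, so any affected patient can be found.

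**Conclusion.** The point holds as a matter of definition. The rule as written counts a category-4 death with no recorded 5, 6 or 7 as new oxygen use, contrary to the SAP's own meaning of being on oxygen, and passes that patient into the Table 42 duration summary.

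It is minor. Each affected patient moves an arm's incidence by 1 to 2 percentage points if the arm has 50 to 100 category-4 patients. The top of the illustrated range, 6 points, needs three such deaths among 50 patients. Those counts are assumptions and start at zero. A reader might conclude that the incidence is inflated by a material amount, but the documents give no count that would show it. The ACTT-1 mortality figures cited in the SAP introduction cover all severities and do not separate deaths without earlier oxygen. Nor is every patient flagged only by an 8 misclassified, given the same-day case.

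**What to change.** In SAP 8.2.4:

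- Define new use as a post-enrollment score of 5, 6 or 7.
- Report category-4 deaths with no recorded 5, 6 or 7 on a separate line, by arm.
- For deaths where the worst-of-day score could hide oxygen started that day, classify by the oxygen-requirement item. Protocol Appendix B, 8.1.2.1 lists this item, and 9.2 says the elements of the scale are captured separately. The documents do not say whether it is completed on the form that records a death. Where it is blank, show the patient as unknown.

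If a composite is intended, keep the threshold and name the outcome as new oxygen use or death in 8.2.4 and Table 42. In either case, state in 6.5 whether the 28-day imputation applies to the new-use block.

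The cost is a few words in 8.2.4, one line in Table 42 and a sentence in 6.5. No new data collection is planned for this.
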